## 1. ABSTRACT

Chinese Americans are one of the fastest growing immigrant groups in the US, who suffer disproportionately high type 2 diabetes (T2D) burden and have poorly controlled T2D. Given the high economic and societal burden of T2D and rapid population growth in Chinese Americans, there is an urgent need for research to develop effective interventions to address T2D burden in this population. Recent evidence suggests the importance of involving and empowering family members in diabetes intervention and calls for family intervention. A mobile health approach such as short message service (SMS) might be a promising way to deliver such family-oriented interventions to the target population given prior studies suggests that Chinese Americans often report challenges to attend in-person lifestyle counseling because of long working hours and lack of sick time from work. A SMS-based intervention provides the flexibility of allowing them to view the intervention at a time and place convenient to them. However, such intervention has not been developed for or tested in Chinese Americans with T2D. This study will serve as the first step to explore an alternative approach for managing T2D in this group. The goal of this pilot study is to examine the feasibility and acceptability of a family-oriented SMS intervention in 30 pairs of Chinese Americans with T2D and their family members. Participants will be randomized to one of 2 arms (n=15 pairs each): 1) wait-list control and 2) SMS intervention. Both groups will continue to receive standard of care treatment for their T2D. The SMS group will receive brief lifestyle counseling videos via SMS links. At the end of the study, the wait-list control group will be provided the opportunity to receive the counseling videos. Measurements will be obtained at baseline, 3, and 6 months. The primary outcome is feasibility and acceptability, and secondary outcomes include HbA1c, self-efficacy, and diabetes self-management behaviors. Findings from this pilot study will inform a larger full-scale R01 efficacy trial of the SMS intervention, and ultimately, an implementation study in the real-world setting. This project can serve as a program model for other chronic disease interventions in Chinese Americans that require lifestyle modification (e.g., prediabetes, hypertension), or for disparities research in other high-risk immigrant populations (e.g., South Asians, Hispanic Americans).

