### 3. METHODS AND PROCEDURES

#### 3.1 Study Design

The proposed study is a pilot randomized controlled trial (RCT) of 6 months duration, with measurements at baseline, 3, and 6 months. Participants will be randomized to one of 2 arms (n=15 pairs each): 1) wait-list control; or 2) SMS intervention.

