#### 3.3. Characteristics of the Research Population

We will recruit **60 participants for this project**, including 30 T2D Chinese patients and 30 corresponding family members. Family member is broadly defined as any support person who the patient considers plays a vital role in their diabetes self-management and would be interested in receiving such interventions. This can be spouse, adult children, siblings, or friends.

**Inclusion criteria for patient participants:** To be eligible for the study, patient participants must: 1) self-identify as Chinese immigrant or Chinese American; 2) be between the ages of 18 and 70; 3) be able to speak and understand Mandarin; 4) self-report a diagnosis of T2D; 5) baseline HbA1c  $\geq 7\%$ ; 6) be currently using WeChat; 7) be willing to receive WeChat or text messages regarding T2D management; 8) express strong interest and confidence in finishing watching 2 diabetes videos each week for a total of 12 weeks; 9) be motivated to make lifestyle changes to control their diabetes; and 10) have a family member or friend be willing to participate in the study to learn about T2D to better support them.

**Inclusion criteria for family/friend participants:** Family/friend participants must 1) self-identify as Chinese immigrant or Chinese American; 2) be between 18-70 years old; 3) be able to speak and understand Mandarin; 4) be currently using WeChat or text messages; 5) be willing to receive WeChat or text messages regarding T2D management and learn how to better support the patient with T2D; 6) express strong interest and confidence in finishing watching 2 diabetes videos each week for a total of 12 weeks; and 7) be motivated to support their family/friend to make lifestyle changes to control their diabetes.

**Exclusion criteria for both patient and family/friend participants:** Individuals will be excluded from participation if they meet any of the following: (1) unable or unwilling to provide verbal consent; (2) unable to participate meaningfully in the intervention (e.g., uncorrected sight and hearing impairment); (3) unwilling to accept randomization assignment; (4) pregnant, plans to become pregnant in the next 6 months, or who become pregnant during the study, (5) breastfeeding, or (6) live in a facility or other health care setting where they have no control over diabetes self-management.

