### Primary & Exploratory Outcomes

**Primary outcome: Feasibility:** Feasibility will be examined by calculating the percent of videos sent that are watched. We will also assess the feasibility by determining whether we are able to meet our recruitment goal of 30 Chinese American families and reach 80% retention rate.

**Acceptability:** Acceptability will be assessed using a satisfaction questionnaire adapted from a prior SMS intervention study.

**Secondary outcomes:** Consistent with our conceptual model (Fig. 1), we will also measure HbA1c, self-efficacy, and diabetes self-management behaviors at each time points (baseline, 3-, and 6-months). All of these scales have been used and validated in the Chinese population.

1. **HbA1c:** As part of the usual care, patients with T2D receive a HbA1c blood test at their doctors' office every 3-6 months. To minimize participants' burden, we will not conduct additional blood tests for this study. Instead, we will abstract the HbA1c testing results from the medical record at the participant's health care facility. Once we obtain the consent from participants, we will contact their doctors' offices for HbA1c results.

2. **Self-efficacy:** We will use the well-validated Stanford Diabetes Self-Efficacy Scale to measure participants' confidence to manage T2D. This instrument contains 8 items and asks participants to rate their confidence level in performing specific self-management behaviors, using 10-point Likert scale ranging from 1 (not at all confident) to 10 (totally confident).
3. **Diabetes Self-Management Behaviors:** We will administer the adapted Summary of Diabetes Self-Care Activities (SDSCA) measure to assess participants' adherence to diabetes self-management behaviors. This scale consists of 13 items and asks participants to describe their diabetes self-care activities over the past 7 days.
4. **Dietary Intake:** Informed by a previous study in Chinese Americans, we will use the adapted Mediterranean Dietary Screener to estimate dietary intake behaviors in our participants at baseline, 3- and 6-months.

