## **7. DATA ANALYSIS AND DATA MONITORING**

### **7.1 Data Analysis**

**Data analysis for Aim 1. Feasibility and acceptability:** Feasibility will be examined by calculating the percent of videos sent that are watched. We will also report the actual enrollment and retention rate. Acceptability will be examined by calculating percent of participants who report satisfaction with our intervention using a questionnaire adapted from a prior SMS intervention study.

**Data analysis for Aim 2.** We will employ the “intent to treat” (ITT) approach in analyses. We will perform a detailed descriptive analysis of all the data collected in the study. These preliminary descriptive statistics will be used to 1) check accuracy and completeness of inputted data, 2) describe univariate distribution of each variable at baseline, and 3) examine the associations between variables. We will also explore features of the data (e.g., amount and pattern of missing data, outliers, excess zeros, departures from distributional assumptions) to determine whether special techniques are needed.

**Aim 2: Proof of concept regarding the potential efficacy of the intervention for glycemic control.** We will test whether the 2 groups are comparable on baseline sociodemographic, health characteristics, and levels of acculturation. If significant differences are found, we will include the variables as covariates in the models. Between group and group by time interaction effects will be examined graphically and via linear mixed modeling for HbA1c. Calculated effect sizes will be used for sample size estimation needed for a two-sided alpha of 0.05 and power of 0.80 for the larger scale R01 study.

**Exploratory Aim: Explore the mediators of the SMS intervention.** Although underpowered, we will perform exploratory analyses of candidate mediators to evaluate the merit of further testing in a larger, adequately powered study. We will perform mediation analyses to determine whether self-efficacy and adherence to diabetes self-management explain significant variance in improvements in HbA1c.

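### Section 7.1 sizes the R01 from the HbA1c effect observed in about 12 to 15 patients per arm, so the R01 cannot be relied on to have its stated 80% power

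*Combined protocol and SAP*

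**What the plan says.** Under Aim 2, section 7.1 (Data Analysis) names the analysis: "Between group and group by time interaction effects will be examined graphically and via linear mixed modeling for HbA1c". The next sentence says what its result is for: "Calculated effect sizes will be used for sample size estimation needed for a two-sided alpha of 0.05 and power of 0.80". The abstract gives the same purpose in general terms: "Findings from this pilot study will inform a larger full-scale R01 efficacy trial of the SMS intervention".

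The amount of HbA1c information is set elsewhere:

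- Section 3.1: "Participants will be randomized to one of 2 arms (n=15 pairs each): 1) wait-list control; or 2) SMS intervention".
- Section 3.3 counts 60 participants, "including 30 T2D Chinese patients and 30 corresponding family members". Under section 4.3 only the patients contribute HbA1c.
- Primary & Exploratory Outcomes (section 4.3) makes it a feasibility criterion "whether we are able to meet our recruitment goal of 30 Chinese American families and reach 80% retention rate".
- The same section says of HbA1c that "we will not conduct additional blood tests for this study". Values come from usual-care tests done every 3 to 6 months.

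The text available for review gives no worthwhile HbA1c difference, no SD, no confidence bound for the effect, and no rule for an estimate that is zero or in the wrong direction. Section 7.1 calls the mediator analysis underpowered but puts no such caution on the sample-size step.

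**The concern.** The required sample size varies with the inverse square of the effect size fed into it. A pilot that overestimates the effect by chance produces an R01 that is too small. One that underestimates it produces an R01 that is too large, or none at all. These errors do not cancel: an oversized trial can gain at most 20 points of power over its 80% label, while an undersized one can lose most of it. With so few patients per arm the observed effect is largely noise, so the 80% figure would not describe the trial that is run.

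The stake is the R01. It could be underpowered without anyone seeing it, or a useful intervention could be dropped because the pilot estimate fell on the wrong side of zero.

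**Working it through.** **Inputs.** From the document: 15 patients per arm (section 3.1), 80% retention target (section 4.3), and two-sided alpha 0.05 with power 0.80 (section 7.1). The target gives 0.80 × 15 = 12 per arm. It is a target, not a dropout forecast. The document states no R01 size or effect, so there is no figure to reproduce. Assumptions: true effect d of 0.2 to 0.8 SD of follow-up HbA1c, and baseline correlation r of 0 (unadjusted) or 0.7. ANCOVA stands in for the planned mixed model.

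**Step 1: precision of the pilot effect.** Half-width = 1.96 × √[(2/n)(1 − r²)].

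| Patients per arm | Unadjusted | r = 0.7 |
|---|---|---|
| 15 | 1.96 × √(2/15) = 0.72 SD | 0.51 SD |
| 12 | 1.96 × √(2/12) = 0.80 SD | 0.57 SD |
| 8 (illustration only) | 0.98 SD | 0.70 SD |

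With t quantiles the unadjusted values at 15 and 12 are 0.75 and 0.85. An observed effect of 0.5 SD from 15 per arm has a 95% CI of −0.23 to 1.22.

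**Step 2: why this costs power.** Per-arm size is n = 2(1.960 + 0.842)²/d² = 15.70/d². For d = 0.4 this is 98.1, so 99. The standard error at 15 per arm is √(2/15) = 0.365. Move the estimate half a standard error either way:

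- Up, to 0.583: n = 15.70/0.339 = 46.3, so 47. Power at the true 0.4 is Φ(0.4√(47/2) − 1.96) = Φ(−0.02) = 49%.
- Down, to 0.217: n = 15.70/0.0473 = 332, so 333. Power is Φ(0.4√(333/2) − 1.96) = Φ(3.2), above 99%.

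**Step 3: simulation of the stated rule.** There were 100,000 pilots per setting. Each pilot with a favourable estimate sizes an R01 at 80% power, and its power is then evaluated at the true effect. Cells show mean true power, then the chance that power is below 80%.

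| True d | 15/arm, unadjusted | 12/arm, unadjusted | 15/arm, r = 0.7 | 12/arm, r = 0.7 |
|---|---|---|---|---|
| 0.2 | 49.7%, 70.7% | 46.5%, 73.0% | 57.1%, 64.7% | 54.6%, 66.6% |
| 0.4 | 65.3%, 58.1% | 62.7%, 60.3% | 70.5%, 54.2% | 68.4%, 55.7% |
| 0.8 | 74.7%, 50.9% | 73.6%, 51.3% | 77.1%, 49.0% | 76.2%, 49.3% |

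Further results at d = 0.4 and 15 per arm:

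| | Unadjusted | r = 0.7 |
|---|---|---|
| Estimate zero or wrong-signed | 13.5% | 6.5% |
| R01 power under 50%, given a favourable estimate | 37.1% | 28.5% |
| Interquartile range of planned n per arm | 33 to 229 | 23 to 118 |
| n per arm needed | 100 | 51 |

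The simulation's 100 compares with 99 from the normal formula. A separate run of 400,000 unadjusted pilots per setting at 15 per arm gave mean power of 59%, 65%, 69% and 75% at d = 0.3, 0.4, 0.5 and 0.8.

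**Step 4: the alternative rule.** Fix the difference at 0.4 true SDs and take only the SD from the pilot (28 df, 15 per arm). Power is evaluated at that difference.

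| | SD point estimate | One-sided 80% upper limit for SD |
|---|---|---|
| Mean power | 78.0% | 86.7% |
| Power under 80% | 53.4% | 20.1% |
| Median n per arm | about 97 | 126 |

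With the SD point estimate, power is under 50% in about 1% of cases (2% at 22 df), and the interquartile range of n is 81 to 116. The upper limit multiplies the SD by 1.139, and 97 × 1.139² = 126.

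**The case against.** **It is a pilot, and the consequence lies outside it.** True. No estimate, test or participant in this study is affected. That limits the severity but does not remove the point, because section 7.1 commits to this use of the result.

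**The sentence does not say point estimate only.** Also true. But it names no other input, no bound and no adjustment. Followed as written, it leaves the calculated effect as the only quantity to put into the formula.

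**The alternative is shown at its best case, where the true effect equals the fixed difference.** This is the strongest objection. With n = 99 and the SD known, power is Φ(d√49.5 − 1.96):

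| True d | Fixed at 0.4 SD | Pilot-effect rule, mean (15/arm, unadjusted, favourable) | Same, only if n ≤ 200 per arm |
|---|---|---|---|
| 0.2 | 29% | 50% | not run |
| 0.3 | 56% | 59% | 39% |
| 0.4 | 80% | 65% | 52% |
| 0.5 | 94% | 69% | 61% |

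Below the fixed difference, the pilot-effect rule averages more power, but part of that comes from very large trials. At d = 0.3 its 90th percentile is 1,806 per arm. If only trials of at most 200 per arm go ahead (an assumption), the advantage at 0.3 reverses. What stands is that the alternative guarantees power for a chosen difference, not for the unknown true effect.

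**The chance of falling below 80% discriminates poorly.** This stands. It is about 53% under the alternative with an SD point estimate, close to several values under the current rule. Mean power, the chance of power under 50% and the spread of n are the informative contrasts.

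**The settings are assumed.** This stands too. The 8-per-arm case is only an illustration, and a mixed model would also use partial data.

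**Conclusion.** The concern holds. In every setting of the main simulation (0.2 to 0.8 SD, 12 to 15 per arm, favourable pilot estimate), an R01 sized by the stated rule has mean true power below 80%: about 47% to 75% unadjusted and 55% to 77% at r = 0.7. Its planned size can differ several-fold by chance. Baseline adjustment reduces the problem without removing it.

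The shortfall shrinks as the true effect grows. At 0.8 SD with r = 0.7 it is marginal: t-based calculations give 76% to 78%, and a normal approximation about 80%. The conclusion rests on assumed true effects and correlations, on ANCOVA as a stand-in for the mixed model, and on every favourable pilot leading to an R01. Fewer usable HbA1c values would make it worse: at 8 per arm, d = 0.4, unadjusted, mean power is 58% and 21% of estimates are zero or wrong-signed. It should be fixed, but it does not touch the pilot's primary results.

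**What to change.** Replace the sample-size sentence under Aim 2 in section 7.1 with:

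> The R01 will be sized (two-sided alpha 0.05, power 0.80) on a clinically worthwhile HbA1c difference fixed before pilot results by arm are seen. The pilot will supply the HbA1c SD (with a stated allowance for its uncertainty), the baseline to follow-up correlation, retention, and the proportion with an HbA1c value at each visit. The pilot HbA1c difference will be reported with its 95% CI as estimation only.

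The sponsor chooses the difference and the SD allowance. The allowance matters because the 95% CI for the SD runs from about 0.79 to 1.35 times the estimate at 15 per arm, and from 0.77 to 1.42 times at 12.

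The cost is one sentence and no new data collection. The R01 may be larger: with the one-sided 80% upper limit as the allowance, median n per arm rises from about 97 to 126 at 0.4 SD. The R01 would also have less than the designed power for any true effect below the chosen difference, but that would be an explicit choice.

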## Data monitoring

Ongoing quality control will include regular data verification and protocol compliance checks. An ongoing review of study procedures will be done to ensure that the privacy of subjects and

confidentiality of data is not violated. Weekly meetings will be held between [name] and [name] and other research staff involved in the project to review the progress of subjects enrolled in the study.

**The whole team will provide oversight for the following study procedures:**

- Monitoring the safety of the subjects (e.g., review the research protocol and plans for data and safety monitoring)
- Evaluate the progress of the clinical trial, including periodic assessments of data quality and timeliness, subject recruitment, accrual and retention, subjects risk versus benefit, performance of the recruitment site, and other factors that can affect study outcome
- Maintaining the confidentiality and integrity of the data
- Reports of critical or adverse events from research staff. The PI will receive these reports on an event-by-event basis and will inform the whole study team of all such reports
- Make recommendations to the IRB and investigators concerning continuation or conclusion of the trial.

## **9. STUDY RECORDS RETENTION AND DATA SHARING**

We are firmly committed to sharing data with the scientific community so that the data generated from this study can be fully utilized for research. Provided below is the proposed data-sharing plan:

1. We will publish the detailed methodology used for this study. Aggregated statistics will be provided to the broad scientific community via a journal's website or to an individual investigator/team upon request.
2. We will release the data generated from all study participants to qualified researchers who wish to collaborate with the investigators from our study. Investigators who wish to collaborate should submit a proposal that will be reviewed using criteria similar to those used by the NIH for scientific merit and human subject protection. All data should be used for research only. No data will be provided that could potentially disclose the identities of study participants.

NIH may release new policies regarding data sharing during the study period. We will be willing to discuss such policies with NIMHD program officers and modify the data-sharing plan detailed above.

